0316-ASG / NEOMUN

NCT03197467

Neoadjuvant anti PD-1 immunotherapy in resectable nonsmall cell lung cancer

Short title:	NEOMUN
Sponsor:	AIO-Studien-gGmbH [name], Germany
Coordinating Investigator (LKP)	[name] [name], Germany
EudraCT Nr.:	2017-000105-20
Protocol identification number:	0316-ASG
Protocol version:	Version 5.0 (22-SEP-2020)

Confidentiality

The contents of the protocol are confidential and may neither be communicated verbally nor in writing without the agreement of the study sponsor.

Contact Addresses

Page 3/102

AIO-Studien-gGmbH

Approval of the Protocol

24. 09 20 20 Date (DD Month YYYY)

SE 20 D Month Y

0316-ASG / NEOMUN

EudraCT-No. 2017-000105-20 Version 5.0, 22-SEP-2020 Page 4/102

Investigator's Agreement

I have read the attached protocol entitled

"Neoadjuvant anti PD-1 immunotherapy in resectable non-small cell lung cancer [NEOMUN]"

Version 5.0, 22-SEP-2020

and agree to abide by all provisions set forth therein.

I agree to comply with the International Conference on Harmonization Tripartite Guideline on Good Clinical Practice all applicable national regulations as well as the requirements of the appropriate Institutional Review Board/Independent Ethics Committee and any other institutional requirements.

I agree to ensure that the confidential information contained in this document will not be used for any purpose other than the evaluation or conduct of the clinical investigation without the prior written consent of the study sponsor.

I consent to report every serious clinical adverse event as well as any other adverse event as specified in the safety section of this protocol to the safety desk within 24 hours after awareness, whether it is related to study medication or not.

Date (DD Month YYYY)

0316-ASG / NEOMUN

EudraCT-No. 2017-000105-20 Version 5.0, 22-SEP-2020

Synopsis

Protocol No.	0316-ASG		
Protocol Version	Final 5.0		
Title	Neoadjuvant anti PD-1 immunotherapy in resectable non-		
	small cell lung cancer [NEOMUN]		
EudraCT No.	2017-000105-20		
National Coordinating	[name]		
Investigator	Thoraxklinik – Universität Heidelberg		
	[name]		
	[name]		
Sponsor	AIO-Studien-gGmbH		
openeer	[name]		
Study design	The study is designed as an open-label, single arm, prospective,		
	monocenter, phase II study of pembrolizumab in a neoadjuvant		
	setting in patients with non-small cell lung cancer of Stage II/IIIA		
	suitable for curative intent surgery		
Indication	Resectable NSCLC stage II/IIIA		
Proposed countries /	Germany		
Total number of sites	Number of sites total: 1		
Primary objective	To assess feasibility and safety of a neoadjuvant application of		
	pembrolizumab		
	To assess antitumor activity of pembrolizumab with regard to		
	clinical and pathologic tumor response		
Secondary objectives	To assess the impact of neoadjuvant pembrolizumab on patient		
	disease free and overall survival.		
Exploratory	To explore potential predictive biomarkers for pembrolizumab		
objectives	efficacy		
	Immune cell imaging:		
	 immune cell infiltrates in and around the resected tumor 		
	 tumor tissue- and serum cytokine profiles 		
	 Hypothesis generation on potential biomarkers predicting efficacy of pembrolizumab using multi-OMICS analysis 		
Planned sample size	N=30.		

Inclusion criteria	1. Cooperation and willingness to complete all aspects of the
	study
	2. Signed and dated written informed consent must be given prior to study inclusion
	3. Histological or cytological confirmed NSCLC.
	4. Clinical stage II-IIIA according to the TNM classification, 7th
	edition.
	stage IIIa: T1/T2 N2 (IIIa ₁₋₃ Robinson classification)
	5. Adequate disease staging by PET/CT performed and
	resectability established.
	6. At least 1 measurable lesion according to RECIST 1.1
	7. Age ≥ 18 years
	8. ECOG performance status 0 - 1
	9. Female subjects of childbearing potential must be willing to use
	an adequate method of contraception as outlined in in the
	protocol, for the course of the study through 120 days after the
	last dose of study medication.
	Note: Abstinence is acceptable if this is the usual lifestyle and
	preferred contraception for the subject.
	Female subject of childbearing potential should have a
	negative urine or serum pregnancy within 72 hours prior to
	receiving the first dose of study medication. If the urine test is
	positive or cannot be confirmed as negative, a serum
	pregnancy test will be required.
	10. Male subjects of childbearing potential must agree to use an
	adequate method of contraception as outlined in protocol,
	starting with the first dose of study therapy through 120 days
	after the last dose of study therapy.
	Note: Abstinence is acceptable if this is the usual lifestyle and
	preferred contraception for the subject.
	11. Adequate bone marrow function, liver and renal function:
	a. Absolute neutrophil count ≥ 1.5 x 10 ⁹ /L
	b. Thrombocytes ≥ 100 x 10 ⁹ /L
	c. Hemoglobin \geq 9 g/dL without transfusion or EPO
	dependency (within 7 days of assessment)

	d. INR < 1.4 and PTT < 40 seconds during the last 7				
	days before therapy				
	e. Bilirubin < 1.5 x upperlimit of normal				
	f. AST (GOT) and ALT (GPT) < 2.5 x ULN				
	g. Albumin ≥ 2.5 mg/dL				
	h. Serum creatinine OR Measured or calculated				
	creatinine clearance (GFR can also be used in place				
	of creatinine or CrCI):				
	≤1.5 X upper limit of normal (ULN) OR				
	≥60 mL/min for subject with creatinine levels				
	> 1.5 X institutional ULN				
	12. adequate lung and cardiac function for intended lung resection				
	according to German S3 guideline				
Exclusion criteria	1. Anticancer treatment during the last 30 days prior to start of				
	treatment, including systemic therapy, radiotherapy or major				
	surgery				
	2. Participation in a clinical trial within the last 30 days prior to				
	study treatment				
	3. History of allogeneic tissue/solid organ transplant				
	4. Has a history of (non-infectious) pneumonitis that required				
	steroids or current pneumonitis.				
	5. Evidence of interstitial lung disease.				
	 cT4 tumor Symptomatic acute cardiovascular or cerebrovascular disease 				
	 Symptomatic acute cardiovascular or cerebrovascular disease Known active HBV, HCV or HIV infection 				
	 9. Has any other active infection requiring systemic therapy. 				
	10. Patients with active tuberculosis				
	11. Prior therapy with an anti-Programmed cell death protein 1				
	(anti-PD-1), anti-Programmed cell death-ligand 1 (anti-PD-L1),				
	anti-PD-L2, anti-CD137 (4-1BB ligand, a member of the Tumor				
	Necrosis Factor Receptor [TNFR] family), or anti-Cytotoxic T-				
	lymphocyte-associated antigen-4 (anti-CTLA-4) antibody				
	(including ipilimumab or any other antibody or drug specifically				
	targeting T-cell co-stimulation or checkpoint pathways)				

12. A diagnosis of immunodeficiency or patient is receiving chronic systemic steroid therapy any other of or form immunosuppressive therapy within 7 days prior to the first dose of trial treatment. 13. Patient has had a prior monoclonal antibody within 4 weeks prior to study Day 1 14. Patient has had prior chemotherapy, targeted small molecule therapy, or radiation therapy within 2 weeks prior to study Day 1 or who has not recovered (i.e., \leq Grade 1 or at baseline) from adverse events due to a previously administered agent. [Note: Subjects with \leq Grade 2 neuropathy are an exception to this criterion and may qualify for the study. If subject received major surgery, he/she must have recovered adequately from the toxicity and/or complications from the intervention prior to starting therapy.] 15. Has an active autoimmune disease requiring systemic treatment within the past 3 months or a documented history of clinically severe autoimmune disease, or a syndrome that requires systemic steroids or immunosuppressive agents. Subjects with vitiligo or resolved childhood asthma/atopy would be an exception to this rule. Subjects that require intermittent use of bronchodilators or local steroid injections would not be excluded from the study. Subjects with hypothyroidism stable on hormone replacement or Sjorgen's syndrome will not be excluded from the study. 16. Has received a live vaccine within 30 days prior to the first dose of trial treatment. [Seasonal influenza vaccines for injection are generally inactivated flu vaccines and are allowed; however intranasal influenza vaccines (e.g., Flu-Mist®) are live attenuated vaccines, and are not allowed.] 17. Has known hypersensitivity to pembrolizumab or any of constituents of the product. 18. Other active malignancy requiring treatment Exceptions include basal cell carcinoma of the skin or squamous cell carcinoma of the skin that has undergone potentially curative therapy or in situ cervical cancer.

 19. Lactating or pregnant women, women of child-bearing potential who do not agree to the usage of highly effective contraception methods (allowed methods of contraception, meaning methods with a rate of failure of less than 1% per year are implants, injectable contraceptives, combined oral contraceptives, intrauterine pessars (only hormonal devices), sexual abstinence or vasectomy of the partner). Women of childbearing potential must have a negative pregnancy test (serum β-hCG) at Screening. 20. Any psychiatric illness that would affect the patient's ability to understand the demands of the clinical trial 21. Patient has already been recruited in this trial 22. Patient who has been incarcerated or involuntarily institutionalized by court order or by the authorities § 40 Abs. 1 S. 3 Nr. 4 AMG. 23. Patients who are unable to consent because they do not understand the nature, significance and implications of the clinical trial and therefore cannot form a rational intention in the light of the facts [§ 40 Abs. 1 S. 3 Nr. 3 AMG].
Pembrolizumab at fixed dose
Pembrolizumab 200 mg q3w i.v. for 2 cycles
After completion of immunotherapy lobectomy/bilobectomy with
curative intent is scheduled.
Survival prognosis in non-small cell lung cancer is strongly disease stage dependent. Patients diagnosed with clinical stage IA have a 5-year survival rate of 82% compared to 6% in patients with stage IV disease [1]. Surgery with curative intent is the standard treatment approach in stage I and II patients and a subgroup of stage III patients. Despite radical tumor resection this treatment approach still is associated with a considerable risk of disease relapse in particular in stage II and IIIA disease. The overall 5-year relapse rate following curative intent surgery is 52% [2]. Standard adjuvant therapy was shown to postpone tumor recurrence by 4-5 month. However, total rate of tumor relapse was not suppressed by

adjuvant therapy. Meta-analysis of clinical trial data indicates that
adjuvant chemotherapy or radio-chemotherapy significantly
increase overall survival. However, the effect is small and accounts
for a 4% improvement in the 5-year overall survival rate.
Neoadjuvant chemotherapy is an alternative standard treatment
approach and typically consists of 3 cycles of platinum-based
combination chemotherapy. Comparable to the adjuvant setting a
neoadjuvant approach confers a 5% increase in the 5-year survival
rate [3]. In terms of efficacy no difference between a pre- or
postoperative chemotherapy approach can be determined [4].

In the light of the efficacy results it is clear, that improved multimodal treatment strategies are direly needed in order to improve long term survival following curative intent surgery. Immunotherapies made a large impact in the treatment of advanced stages of malignant diseases leading to marketing approvals for several tumor entities including NSCLC. Neoadjuvant immunotherapy by application of anti-PD-1 targeting antibodies is a logical conclusion based on the treatment reality described above. Clinical data on neoadjuvant treatment is scarce but encouraging and several trials investigating anti-PD-1/PD-L1 checkpoint inhibition (e.g. nivolumab, durvalumab, atezolizumab) are ongoing.

Consequently, the scope of this trial will be the generation of pilot data on efficacy, safety and feasibility of neoadjuvant anti-PD-1 immunotherapy by pembrolizumab. The research endeavor will be flanked by a translational research program to elucidate potential predictive biomarkers and to investigate the mode of action of anti PD-1 treatment in NSCLC patients.

Rationale for sample size and tests to be used A phase II approach will be used to generate preliminary hypothesis generating data. No formal sample size estimation has been performed. The scope is to gather information on feasibility, safety and efficacy.

Target sample size is N=30.

	The rationale for the sample size of this trial is based on ethical,
	clinical as well as scientific considerations. The neo-adjuvant
	treatment approach with an immune check-point inhibitor is highly
	experimental with only limited data on safety and feasibility
	available. Therefore, only a small number of patients should be
	subjected to this experimental treatment. Nevertheless, the sample
	size should allow the generation of statistically meaningful
	evidence for feasibility and safety to permit the decision to further
	develop this treatment approach.
	With a sample size of N=30 and assuming that the number of
	events follows a binomial distribution B(30,p), events with an
	incidence rate $p > 9.5\%$ will be observed at least once with a 95%
	probability. This observation limit will exclude individual
	pembrolizumab related SAEs but covers most of the historical
	reference events/rates of the primary endpoints in this trial as well
	as the early stopping rule.
	The degree of the potential evidence provided by a sample size of
	N=30 is summarized in the statistics section of the protocol.
Endpoints / Statistical	The trial design will be a phase II trial, with descriptive outcome
analysis	assessments of:
	Primary endpoints:
	 frequency and severity of adverse events including peri-
	and post-operative complications (grade 2-4 AEs
	according to NCI-CTCAE V4.03)
	 number of patients treated in compliance with
	protocol
	Tumor response evaluation
	Clinical response parameters:
	Clinical response parameters: \circ response rates (Δ tumor size / lymph node size),
	 Clinical response parameters: o response rates (∆ tumor size / lymph node size), according to RECIST 1.1 criteria
	 Clinical response parameters: o response rates (∆ tumor size / lymph node size), according to RECIST 1.1 criteria o ∆ PET-activity (standardized uptake value [SUV])
	 Clinical response parameters: o response rates (∆ tumor size / lymph node size), according to RECIST 1.1 criteria
	 Clinical response parameters: o response rates (∆ tumor size / lymph node size), according to RECIST 1.1 criteria o ∆ PET-activity (standardized uptake value [SUV])

	Secondary endpoints:disease free survivaloverall survival	
Study plan	FPI	Q2/2018
	LPI	after approx. 36 month (Q2/2021)
	LPO	after approx. 40 month
		(Q4/2021)
	EoS (after 24 month FU of LPO)	after approx. 64 month
		(Q4/2023)

Schedule of Study Assessments

Study Phase	Screening	Treatme	Treatment phase		Dis-charge	End of treatment	Follow-up
Procedure	SCR	V1	V2	PS	D	EOT	FU1 – FUx
Time windows	Day - 28	Day 1	V2 Day 21 +/- 3 days	Day 43-50	Day 60-74	6 wks. after	every 3
	to 0	Day I	Day 21 +/- 5 uays	Day 43-50	Day 00-74	surgery	months
Informed consent	 					Surgery	monting
Demographics	X X						
(age, gender, race)							
Tumor diagnosis	Х						
Cancer history	Х						
Medical history (incl. smoking status)	Х						
Previous treatments	X						
Tumor assessments (PET)-CT, RECIST 1.1	Х			Х			
Tumor staging (PET-CT, MRI brain)	Х						
Chest X-ray	Х		Х	Х	Х	Х	
Cardiac evaluation (12-lead ECG)	Х		(X) ¹	Х		Х	
Physical examination ²	Х		Х	Х	Х	Х	
Body weight and height / BSA ³	Х		Х	Х		Х	
Vital signs (BP, HR, body temperature)	Х	(X) ⁸	х	Х	х	х	
Lung function test blood gas values	Х		х	х		х	
ECOG status	Х		Х	Х		Х	
Pregnancy test (if applicable)	Х	(X) ⁸					
Hematology ⁴	Х	(X) ⁸	Х	Х	Х	Х	
Coagulation	Х	(X) ⁸	Х	Х	Х	Х	
Clinical chemistry ⁵	Х	(X) ⁸	Х	Х	Х	Х	
tumor marker	Х			Х		Х	
TSH ⁶	Х		Х	Х	Х	Х	
In- / Exclusion criteria	Х						
Biomarkers (blood sample)		Х	Х	Х	Х	Х	
Tumor tissue ⁹	Х				Х		
HR-QoL	Х			Х		Х	
Treatment (V1/V2)		Pembrolizumab 200 mg i.v	Pembrolizumab 200 mg i.v				

0316-ASG / NEOMUN

Study Phase Procedure	Screening	Treatment phase		Pre- Surgery	Dis-charge	End of treatment	Follow-up
Visit	SCR	V1	V2	PS	D	EOT	FU1 – FUx
Time windows	Day - 28 to 0	Day 1	Day 21 +/- 3 days	Day 43-50	Day 60-74	6 wks. after surgery	every 3 months
Concomitant medication	Х		Continuously				
Concomitant procedures	Х		Continuously				
Adverse events	Х	Continuously			X ⁷		
Subsequent cancer therapy							Х
Survival status							Х

¹ if clinically indicated. Consult a specialist if clinically abnormal and exclude any immune-related myocarditis.

² Full examination is required at baseline and end of treatment. Focused clinical examination shall prevail throughout the course of treatment.

³ Body height will only be measured at screening.

⁴ Full blood count including blood differential test will be performed at baseline, after start of treatment (V2) and further indicated time points throughout treatment and at end of study.

⁵ Sodium, potassium, calcium, magnesium, phosphate, AST, ALT, PTT/INR, LDH, total bilirubin, creatinine, creatinine clearance, albumin, tumor marker CEA, Cyfra 21-1

⁶ To be done at baseline and 3 weeks after start of treatment (V2) and further indicated time points throughout treatment and at end of study. If rising TSH is detected, a full assessment of fT3 and fT4 shall be performed and signs of hormone depletion shall be monitored clinically.

⁷ Follow-up of ongoing SAEs until resolution or stabilization. Serious adverse events are recorded until 90 days after last dose of IMP or for 6 weeks after surgery if the subject initiated new anticancer therapy (e.g. radiochemotherapy). Pregnancies occurring in a study subject are recorded from time of signed informed consent until 120 days after last dose of IMP.

⁸ Repeat assessment if SCR assessment is older than 7 days.

⁹ Post-op. tumor regression grading.

Safety reporting contact information (SAE / Pregnancy)

In the case of a serious adverse event (SAE) or pregnancy safety desk must be contacted within 24 hours.

Contact details for safety reporting are provided in the Investigator Site File.

The safety desk will inform MSD Germany Pharmacovigilance (Email:

) and other appropriate persons about all SAEs, as well as pregnancy and events of clinical interest, within 1 working day of knowledge of the event.

Glossary of Abbreviations

ADR	Adverse drug reaction
AE	Adverse event
AIO	Arbeitsgemeinschaft Internistische Onkologie
ALT (SGPT)	Alanine aminotransferase
AMG	Arzneimittelgesetz (German Drug Law)
ANC	Absolute neutrophil count
AST (SGOT)	Aspartate aminotransferase
AUC	Area under the curve
BP	Blood pressure
BSA	Body Surface Area
CI	Confidence interval
CR	Complete response
CRF / eCRF	Case report form / electronic Case report form
CSR	Clinical study report
СТ	Computed tomography
CTC	Common terminology criteria
CTCAE	Common terminology criteria of adverse events
D	Day
	•
ECG	Electrocardiogram
ECOG	Eastern Cooperative Oncology Group
e.g.	For example
EMA	European Medicines Agency
EOT	End of treatment
etc	Et cetera
FPFV	First patient first visit
FU	Follow up
g	Gram
GCP	Good Clinical Practice
GCP-V	GCP-Verordnung
HR	Heart rate
HR	Hazard ratio
IADL	Instrumental Activities of Daily Living
IB	Investigators' Brochure
ICF	Informed consent form
ICH	International Conference on Harmonization
IDMC	-
	Independent Data Monitoring Committee
i.e.	That is
IMP	Investigational medicinal product
ITT	Intent to treat
i.v. / IV	Intravenous
	kilogram
kg	-
LKP	Leiter der klinischen Prüfung (Co-ordinating Investigator)
LPFV	Last patient first visit
LPLV	Last patient last visit
m ²	Square meter (body surface area)
mAb	
IIIAU	Monoclonal Antibody

mg	Milligram
min	Minute
mL	Milliliter
mm	Millimeter
MRI	Magnetic resonance imaging
NCI	National Cancer Institute
NCT	National Center for Tumor Diseases
NOAEL	no observed adverse effect level
OP	Operation
ORR	Objective response rate
OS	Overall survival
PD	Progressive disease
PD-1	Programmed death receptor 1
PD-L1	Programmed death receptor ligand 1
PFS	Progression free survival
PP	Per Protocol
PR	Partial response
q3w	Every 3 weeks
QoL	Quality of Life
RECIST	Response Evaluation Criteria in Solid Tumors
RICTOR	Rapamycin-insensitive companion of mTOR
SAE	Serious adverse event
SADR	Serious adverse drug reaction
SCR	Screening
SD	Stable disease
SOC	Standard of Care
SUSAR	Suspected unexpected serious adverse reaction
SUV	Standardized uptake value
TBD	To be determined
TTFS	Time to Failure of Strategy
TPS	Tumor Proportion Score
V	Version
WHO	World Health Organization

Table of Contents

CONTACT ADDRESSES			2
APPROVAL OF THE PROTOCOL			3
INVESTIGATOR'S AGREEMENT			4
Synopsis			5

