4.2 Inclusion Criteria

- 1. Cooperation and willingness to complete all aspects of the study
- 2. Signed and dated written informed consent must be given prior to study inclusion
- 3. Histological or cytological confirmed NSCLC
- 4. Clinical stage II-IIIA according to the TNM classification, 7th edition: stage IIIa: T1/T2 N2 (IIIa₁₋₃ Robinson classification)
- 5. Adequate disease staging by PET/CT and brain MRI
- 6. At least 1 measurable lesion according to RECIST 1.1
- 7. Age \geq 18 years
- 8. ECOG performance status 0 1
- Female subjects of childbearing potential (Section 7.6.6) must be willing to use an adequate method of contraception as outlined in Section 7.6.6 – Contraception and Pregnancy, for the course of the study through 120 days after the last dose of study medication.

Note: Abstinence is acceptable if this is the usual lifestyle and preferred contraception for the subject.

Female subject of childbearing potential should have a negative urine or serum pregnancy within 72 hours prior to receiving the first dose of study medication. If the urine test is positive or cannot be confirmed as negative, a serum pregnancy test will be required.

10. Male subjects of childbearing potential (Section 7.6.6) must agree to use an adequate method of contraception as outlined in Section 7.6.6 – Contraception and Pregnancy, starting with the first dose of study therapy through 120 days after the last dose of study therapy.

Note: Abstinence is acceptable if this is the usual lifestyle and preferred contraception for the subject.

- 11. Adequate bone marrow function, liver and renal function:
 - a. Absolute neutrophil count $\ge 1.5 \times 10^9$ /L
 - b. Thrombocytes \geq 100 x 10⁹/L
 - c. Hemoglobin ≥ 9 g/dL without transfusion or EPO dependency (within 7 days of assessment)
 - INR < 1.4 ULN and PTT < 40 seconds during the last 7 days before therapy
 - e. Bilirubin < 1.5 x upper limit of normal
 - f. AST (GOT) and ALT (GPT) < 2.5 x ULN
 - g. Albumin >2.5 mg/dL
 - h. Serum creatinine **OR** Measured or calculated creatinine clearance (GFR can also be used in place of creatinine or CrCl):

≤1.5 X upper limit of normal (ULN) OR

≥60 mL/min for subject with creatinine levels > 1.5 X institutional ULN

12. Adequate lung and cardiac function for intended lung resection according to German S3 guideline

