8.2 Sample Size Calculation

A phase II approach will be used to generate preliminary hypothesis generating data. No formal sample size estimation has been performed. The scope is to gather information on feasibility, safety and efficacy.

Target sample size is N=30

The rationale for the sample size of this trial is based on ethical, clinical as well as scientific considerations. The neo-adjuvant treatment approach with an immune check-point inhibitor is highly experimental with only limited data on safety and feasibility available. Therefore, only a small number of patients should be subjected to this experimental treatment. Nevertheless, the sample size should allow the generation of statistically meaningful evidence for feasibility and safety to permit the decision to further develop this treatment approach.

With a sample size of N=30 and assuming that the number of events follows a binomial distribution B(30,p), events with an incidence rate p > 9.5% will be observed at least once with a 95% probability. This observation limit will exclude individual pembrolizumab related SAEs but covers most of the historical reference events/rates of the primary endpoints in this trial as well as the early stopping rule.

The degree of the potential evidence provided by a sample size of N=30 is summarized in Table 3.

Table 3 Reported reference data and exact CI under a sample size of N=30 [Clopper Pearson
method] [13-15]

Adverse event / endpoint	Reported Frequency	95% CI for sample size of N=30
AE rate in Pembrolizumab monotherapy	97.4%	83.9 - 100.0
trials		
Drug related AE rate in Pembrolizumab	73.7%	54.5 - 88.0
monotherapy trials *		
SAE rate in Pembrolizumab monotherapy	37.2%	20.4 - 56.7
trials *		
Drug related SAE rate in Pembrolizumab	10 %	2.1 – 26.5
monotherapy trials *		
Cumulative rate of the 5 most frequent	9.4%	1.8 – 25.7
SAEs in Pembrolizumab monotherapy		
trials and potential impact on neo-adjuvant		
treatment approach and/or surgery		
[pneumonia (3.0%), pleural effusion		
(1.7%), pneumonitis (1.6%), dyspnea		
(1.6%) and pulmonary embolism (1.5%)] *		
number of patients treated in compliance	80 %	61.4 – 92.3
with protocol / Feasibility of resection and		
early stopping rule [#]		
Radiologic response (CR or PR) per	10 %	2.1 – 26.5
RECIST 1.1 §		
Pathologic response (grade IIb or higher as	43 %	25.2 - 62.3
per Junker criteria) [§]		
* See also section 1.2.4 and IB of pembrolizur	nab	1

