6.3.1 Data Points

- Hematology
 - o basophils absolute
 - o eosinophils absolute
 - o erythrocytes
 - o hemoglobin
 - o leukocytes
- Clinical chemistry and coagulation
 - o ALT
 - o AST
 - o activated partial thromboplastin
 - time
 - albumin absolute
 - o calcium
 - o creatinine

- o lymphocytes absolute
- o monocytes absolute
- o neutrophils absolute
- o platelets
- o creatinine clearance
- o LDH
- o magnesium
- o phosphate
- o potassium
- o prothrombin time relative
- o **sodium**

Adapted from:

STATO3_A Statistical Analysis Plan

Version 6.0, Effective Date 16-Feb-2018

Page 15 of 23

Confidential and intellectual property of Assign DMB. No part of this document or its contents may be duplicated, referenced, published or otherwise disclosed in any form or by any means without prior written consent of Assign DMB.

| TSH | 0 | free T3 |
|-----------------|---|---------|
| total bilirubin | 0 | free T4 |

The following variables will be analyzed descriptively:

• Absolute values by time point

0

0

- Absolute change from screening values by time point •
- Values above and below normal range by time point •

Conversion of laboratory parameters will be performed from a study site specific laboratory unit into the unit to be used in the statistical analysis via the following formula:

Value in analysis unit = value in study site specific unit * conversion factor •

The following units will be used as standard units:

| Parameter | Unit used for Analysis |
|------------------------------------|------------------------|
| Clinical chemistry and coagulation | on |
| ALT | U/I |
| AST | U/I |
| albumin absolute | g/l |
| calcium | mmol/l |
| creatinine | mg/dl |
| creatinine clearance | ml/min |
| LDH | U/I |
| magnesium | mmol/l |
| phosphate | mmol/l |
| potassium | mmol/l |
| prothrombin time relative | % |
| sodium | mmol/l |
| TSH | mU/I |
| total bilirubin | mg/dl |
| free T3 | ng/l |
| free T4 | ng/l |
| Tumor marker | |
| CEA | µg/I |
| Cyfra 21-1 | µg/I |

| Parameter | Unit used for Analysis | | | | |
|------------------------------------|------------------------|--|--|--|--|
| Clinical chemistry and coagulation | | | | | |
| ALT | U/I | | | | |
| AST | U/I | | | | |
| albumin absolute | g/l | | | | |
| calcium | mmol/I | | | | |
| creatinine | mg/dl | | | | |
| creatinine clearance | ml/min | | | | |
| LDH | U/I | | | | |
| magnesium | mmol/I | | | | |
| phosphate | mmol/I | | | | |
| potassium | mmol/I | | | | |

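### Inclusion 11 g states the albumin limit in mg/dL; at 0.025 g/L this sub-item, as written, excludes no one

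*Protocol*

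**What the plan says.** Inclusion criterion 11 of the Protocol is headed "Adequate bone marrow function, liver and renal function" and lists laboratory limits under items a to h. Item g in the Synopsis reads "Albumin ≥ 2.5 mg/dL". Item g in section 4.2 has the same number and unit, with the sign set as an underlined greater-than. Item c of both lists, hemoglobin, is in g/dL: "9 g/dL without transfusion or EPO".

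The SAP does not restate the eligibility limit. Its section 6.3.1 gives the unit for analysing albumin, "albumin absolute | g/l", and uses mg/dL for creatinine and total bilirubin. It also provides for converting site units to analysis units by a factor.

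The inclusion criteria bear on the analysis in three places:

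- SAP 2.11.1 counts a patient as enrolled, and so in the ITT population, once the investigator has answered yes to the eCRF question on eligibility.
- Protocol 8.3.2 and SAP 2.9 and 2.11.2 remove from the per-protocol population a patient who fails a major inclusion criterion. SAP 2.9 describes these as criteria with relevant impact on efficacy. The population is settled at the data review meeting.
- SAP 5 makes the per-protocol population primary for efficacy.

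The summary of changes in Protocol Appendix 7 records a correction to item 11 d in the Synopsis and none to 11 g.

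**The concern.** An inclusion limit is an operative rule: it decides who enters, and it is the yardstick for calling an inclusion criterion violated. A limit written in mg/dL for an analyte that the SAP reports in g/L suggests a unit slip large enough to disable the rule. Because the same unit stands in both lists, neither can be used to correct the other, and an error in reading the PDF is unlikely.

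Either way of applying the item is unsatisfactory. Read literally, it never fails anyone. Read in some other unit by site staff who notice the oddity, the limit that decides eligibility is one that the documents do not contain, and the data review meeting has no written standard for judging whether it was met.

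**Working it through.** **Inputs.** The limit is 2.5 mg/dL (Protocol Synopsis and section 4.2, item 11 g). The SAP analysis unit is g/L (section 6.3.1). The limit is stated, not derived from anything else in the plan, so there is no calculation of the sponsor's to reproduce for it.

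**Step 1: convert the limit.**
2.5 mg/dL × 10 dL/L = 25 mg/L, and 25 mg/L ÷ 1000 mg/g = 0.025 g/L.

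**Step 2: compare it with possible patient values.** The documents give no reference range for albumin. Assume screening values from 5 g/L, taken as extremely low, to 50 g/L. Since 1 g/L = 100 mg/dL:

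- 5 g/L = 500 mg/dL, and 500 ÷ 2.5 = 200 times the limit.
- 50 g/L = 5000 mg/dL, and 5000 ÷ 2.5 = 2000 times the limit.

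Every value in the assumed range passes. The result does not hang on where the range ends, because anything at or above 0.025 g/L passes.

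**Step 3: show the scale of the discrepancy.** Purely as an illustration, and not as a suggested limit, the same digits in g/dL would be 2.5 × 10 = 25 g/L, which is 25 ÷ 0.025 = 1000 times the limit as written. The two readings classify as follows:

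| Albumin (g/L) | Multiple of written limit | As written | Same digits in g/dL |
|---|---|---|---|
| 5 | 200 | pass | fail |
| 10 | 400 | pass | fail |
| 15 | 600 | pass | fail |
| 20 | 800 | pass | fail |
| 25 | 1000 | pass | pass |
| 30 | 1200 | pass | pass |
| 35 | 1400 | pass | pass |
| 50 | 2000 | pass | pass |

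The choice of unit therefore changes eligibility only for patients with low values. The documents do not show how many such patients, if any, were screened.

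**Step 4: check what else depends on the limit.** Protocol 8.2 states that "No formal sample size estimation has been performed". Its observation limit comes from N alone: 1 − 0.05^(1/30) = 0.0950, which agrees with the printed 9.5%. The exact intervals in Table 3 use N=30 and external reference rates. None of these takes albumin as an input.

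**The case against.** The best case on the other side is that this is a typographical slip with little practical effect. The trial has one centre, and staff would probably see that 0.025 g/L is not a meaningful limit. That is plausible, but it is not documented, and it does not supply the rule that staff would then be applying.

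Several stronger readings are tempting, and the documents do not support them.

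- **That the item was the safeguard against patients unfit for resection.** Item 11 concerns bone marrow, liver and renal function. Lung and cardiac fitness for the operation is inclusion 12, and the Synopsis asks under inclusion 5 that resectability be established.
- **That liver function goes unscreened.** Items 11 d to f still set limits on INR and PTT, bilirubin, and AST and ALT. ECOG status of 0 to 1 is also required.
- **That a programmed check would pass everyone.** Neither document describes an edit check on albumin. Eligibility is the investigator's yes-or-no answer, and SAP Listing 16.2.1.4 carries the criterion and the answer, not a laboratory value.
- **That no deviation could ever be raised.** SAP 2.9 leaves its list of relevant deviations open, and SAP Listing 16.2.4.15 shows chemistry values, so the data review meeting could still question a low albumin. What holds is narrower: the item, applied literally, is not violated.
- **That the SAP contradicts the Protocol.** The g/L in the SAP is an analysis unit with conversion allowed. It does not govern eligibility, and albumin tables are unaffected by the wording of 11 g.

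These objections limit the consequence. They leave the defect itself standing, since no other passage corrects the unit.

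**Conclusion.** The point holds in a narrow form. As written in both places, item 11 g is a limit of 0.025 g/L. It excludes no one at any plausible serum albumin and is never violated when read literally. The conversion is exact. The statement that no one is excluded rests on the assumed range of 5 to 50 g/L, but would survive any realistic alternative.

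The effect reaches eligibility under one sub-item and the classification of violations of it. It reaches the per-protocol population only if the data review meeting treats albumin as a major criterion, which the documents leave open. A reader might infer that unsuitable patients were enrolled or that an endpoint is biased; nothing in the documents shows either. This is a minor correction, worth making because the rule is operative and the repair is cheap.

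**What to change.** The sponsor should confirm the intended unit and limit for albumin, then correct item 11 g identically in the Synopsis and section 4.2. The limit need not be expressed in g/L, provided that the unit is right and the two lists agree. When inclusion violations are reviewed at the data review meeting, the confirmed limit should be the one applied. No threshold is proposed here.

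The cost is a text correction in two places and one check of recorded screening values against the confirmed limit. The sponsor classed the comparable correction to 11 d in version 5.0 as non-substantial. If recruitment has closed, a written clarification before the data review meeting would settle how violations are classified.
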